## 2. LIST OF ABBREVIATIONS

See Medicine Glossary:

Date: 8 Apr 2024, Version 1.0

http://glossary

Term	Definition / description		
ADA	Anti-Drug Antibody		
AE	Adverse Event		
AESI	Adverse Event of Special Interest		
BLRM	Bayesian Logistic Regression Model		
BMI	Body Mass Index		
CR	Complete Response		
DLT	Dose Limiting Toxicity		
ECOG	Eastern Cooperative Oncology Group		
EOT	End of Treatment		
ЕоТ	End-of-Text		
RECIST	Response Evaluation Criteria in Solid Tumours		
itRECIST	Response Criteria for Intratumoural Immunotherapy in Solid Tumours		
iRECIST	Immune Response Evaluation Criteria In Solid Tumours		
MTD	Maximum Tolerated Dose		
OR	Objective Response		
ORR	Objective Response Rate		
PKS	Pharmacokinetic parameter set		
PR	Partial Response		
RECIST	Response Evaluation Criteria In Solid Tumours		
REP	Residual Effect Period		
SCS	Screened Set		
TS	Treated Set		
ULN	Upper Limit of Normal		

Proprietary confidential information © 2024 Boehringer Ingelheim International GmbH or one or more of its affiliated companies.

## 3. INTRODUCTION

Date: 8 Apr 2024, Version 1.0

As per ICH E9 (9.1), the purpose of this document is to provide a more technical and detailed elaboration of the principal features of the analysis described in the protocol, and to include detailed procedures for executing the statistical analysis of the primary and secondary variables and other data.

This TSAP assumes familiarity with the Clinical Trial Protocol (CTP), including Protocol Amendments. In particular, the TSAP is based on the planned analysis specification as written in CTP Section 7 "Statistical Methods and Determination of Sample Size". Therefore, TSAP readers may consult the CTP for more background information on the study, e.g., on study objectives, study design and population, treatments, definition of measurements and variables, planning of sample size, randomization.

SAS® Version 9.4 (or a newer version) and Phoenix TM WinNonlin® Version 8.1 (or a newer version) will be used for PK analyses. R version 4.0.1 (or a newer version) and Stan will be used for all analyses related to BLRM. SAS® Version 9.4 (or a newer version) will be used for all other analyses.

Date: 8 Apr 2024, Version 1.0

c44138015-01

Proprietary confidential information © 2024 Boehringer Ingelheim International GmbH or one or more of its affiliated companies.

## 4. CHANGES IN THE PLANNED ANALYSIS OF THE STUDY

As development of BI 1387446 has been terminated, the following further endpoints will not be analysed for the CTR:

Proprietary confidential information © 2024 Boehringer Ingelheim International GmbH or one or more of its affiliated companies.

# 5. ENDPOINTS(S)

## **5.1 PRIMARY ENDPOINT(S)**

The main objective of this trial is to determine the maximum tolerated dose (MTD) for BI 1387446 as single agent (Arm A) and for BI 1387446 in combination with ezabenlimab (Arm B). The number of patients with Dose Limiting Toxicities (DLTs) during the MTD evaluation period will be used to determine the MTD in each arm.

The primary endpoints are:

- MTD based on number of Dose-limiting toxicities (DLTs)
- Number of patients with DLT in the MTD evaluation period

The MTD is defined as the highest dose with less than 25% risk of the true DLT rate being above 33% during MTD evaluation period. For definition of DLTs, see CTP Section 4.1.4.4.

The MTD evaluation period is defined as the first treatment cycle including echocardiographic/MUGA scan measurements acquired on Day 1 of Cycle 2.

For analyses, the MTD evaluation period will be derived as the time from the first administration of study drug to the start of the second treatment cycle, i.e. in more detail as the time from the first administration of (any) trial medication to the start of the 2nd administration of ezabenlimab or 4th administration of BI 1387446 (whatever from the latter two comes first). In the case that the 2nd administration of ezabenlimab and/or the 4th administration of BI 1387446 are not given, the MTD evaluation period ends 90 days after the last administration.

Patients who were replaced during the MTD evaluation period will not be considered for MTD determination. Patients who experience a DLT will not be replaced. The decision on replaced patients will be collected in a separate file and stored in the TMF. Patients that have not been replaced will be referred to as patients evaluable for MTD determination (MTD set).

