3.3.4.1 Discontinuation of trial treatment

An individual patient will discontinue trial treatment if:

- The patient wants to discontinue trial treatment, without the need to justify the decision.
- The patient has repeatedly shown to be non-compliant with important trial procedures and, in the opinion of both, the Investigator and sponsor representative, is not willing or able to adhere to the trial requirements in the future.
- The patient needs to take concomitant medication that interferes with the investigational medicinal product or other trial treatment (Refer to [Section 4.2.2.1](#)).
- The patient can no longer receive trial treatment for medical reasons (such as surgery, adverse events, other diseases, or pregnancy). Recurring radiologic disease progression (Refer to [Section 4.1.2.3](#)).

- Adverse events requiring a permanent discontinuation of trial drugs, e.g. Cytokine release syndrome Grade ≥ 3 Infusion-related reaction to ezabenlimab (BI 754091) Grade ≥ 3 Drug-related AE not recovering to G1/baseline within 12 weeks
 - More than 2 dose reductions of BI 1387446 would be required for management of AEs
 - Immune-related AEs requiring permanent treatment discontinuation as per [Section 10.1.2](#).
- If the patient experiences an infection with SARS-CoV-2 (as confirmed in accordance with local practice/accepted guidelines, see [Section 5.2.3](#)), the patient may resume trial treatment following recovery from SARS-CoV-2 infection if the patient is expected to derive clinical benefit, as agreed between the investigator and sponsor.

Patients in a dose cohort needed to make a dose escalation decision will be replaced in case they discontinued early during Cycle 1 for non-safety related reasons (e.g. unable to attend the protocol defined visits for personal reason, refer to [Section 3.3.4.4](#) below), or trial disruption e.g., measures to control the spreading of COVID-19. These patients will be replaced until the minimum number of patients required for evaluation is reached.

In case of a temporary reason for trial disruption, trial treatment should be restarted if medically justified, refer to see [Section 4.1.4.3](#).

Even if the trial treatment is discontinued, the patient without disease progression remains in the trial and, given his/her agreement, will undergo the procedures for early treatment discontinuation and follow-up as outlined in the [Flow Chart](#) and [Section 6.2.3](#).

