3.3.4.4 Replacement of patients

In Arms A and B, patients withdrawn during the MTD evaluation period for a reason other than having a DLT, or who miss any dose of study medication during the MTD evaluation period, or who miss the echocardiography/MUGA scan measurements acquired on Day 1 of Cycle 2), are not evaluable for the MTD determination. These patients will be replaced if not decided otherwise by the SMC (e.g. because the number of evaluable patients for the current dose cohort is considered high enough for a dose escalation decision). Patients who experience a DLT will not be replaced.

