7.2.2 Primary endpoint analyses

In order to identify the MTD, the number of evaluable patients with DLTs during the MTD evaluation period at each dose level in each arm must be presented. Replaced patients will be excluded from the determination of MTD.

For Arm A and B, the main analysis of the MTD will use the joint 5-parameter BLRM model described above using DLT data from the MTD evaluation period. For this analysis, cross-over patients will only be included while being treated with BI 1387446 monotherapy in Arm A.

The following sensitivity analyses for the analysis of the MTD will be performed to support the determination of the RD-P2:

[figure not shown]
- Separate BLRMs will be used for each escalation arm using all DLT data, not only DLT data from the MTD evaluation period
- The joint BRLM will be evaluated using all DLT data, not only DLT data from the MTD evaluation period

The sensitivity analyses will include all treated patients, including 'backfill' patients and cross-over patients. More details on sensitivity analyses will be specified in the TSAP.

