#### • MTD set:

The MTD set includes all treated patients who are considered evaluable as per CTP, that is, all patients who have completed the required number of administrations of BI 1387446 (and ezabenlimab in arm B) in cycle 1 and who underwent the Echo/MUGA scan in cycle 2 visit 1. In case a patient has not completed the required number of study drug administrations due to DLT(s), he/she will be considered evaluable and included in the MTD set. Patients who cross over from Arm A to Arm B will only be included in the MTD set if they are evaluable in Arm A. The MTD set will be used for the main analysis of the MTD.

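### The SAP defines the MTD set in two incompatible ways: by replacement status in 5.1 and by completed cycle 1 dosing plus echo in 6.4

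*SAP*

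**What the plan says.** **SAP 5.1** excludes patients replaced during the MTD evaluation period and says DLT patients are not replaced. It has replacement decisions recorded in a separate file in the TMF, and then says "Patients that have not been replaced will be referred to as patients evaluable for MTD determination (MTD set".

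**SAP 6.4** defines the set of the same name as "all patients who have completed the required number of administrations of BI 1387446 (and ezabenlimab in arm B) in cycle 1". A second condition is that the echo or MUGA at the first Cycle 2 visit was done. Its one exception is for drug administrations left incomplete because of a DLT. It adds: "The MTD set will be used for the main analysis of the MTD".

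**Protocol 3.3.4.4** treats evaluability and replacement as separate steps. A patient is not evaluable after withdrawal for a reason other than a DLT, any missed dose in the MTD evaluation period, or a missed Cycle 2 Day 1 echo/MUGA. Of such patients it says "These patients will be replaced if not decided otherwise by the SMC", for example when enough evaluable patients are already available.

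**Protocol 3.3.4.1** describes replacement more narrowly. Patients in a cohort needed for an escalation decision "will be replaced in case they discontinued early during Cycle 1 for non-safety related reasons", or because of trial disruption.

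**Protocol 7.2.2** says "Replaced patients will be excluded from the determination of MTD". SAP 7.4.1 has a matching sentence.

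**The concern.** Replacement is a conduct decision; evaluability is a property of the patient's data. Protocol 3.3.4.4 foresees patients who are not evaluable and are not replaced. SAP 5.1 calls these patients evaluable, while SAP 6.4 and the protocol do not.

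Both primary endpoints rest on this set. If the flag followed 5.1, a patient who had one of the three cycle 1 injections and left without a DLT would enter the binomial denominator as a fully observed non-DLT. The number of patients with a DLT would not change. The denominator would grow, the modelled DLT rate would fall, and the model-based MTD could rise. Protocol 3.1.2 intends at most 8 patients per dose level who have completed a cycle, so one patient carries weight.

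**Working it through.** **1. The rules side by side** (patients not replaced)

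| Patient | SAP 5.1 | SAP 6.4, literal | Protocol |
|---|---|---|---|
| One of three injections, leaves without a DLT, SMC waives replacement | in | out | not evaluable (3.3.4.4) |
| Full cycle 1 dosing, no DLT, no Cycle 2 echo | in | out | not evaluable (3.3.4.4) |
| DLT stops dosing, echo done | in | in | not replaced (3.3.4.4) |
| DLT after full dosing, no Cycle 2 echo | in | out | not replaced (3.3.4.4); a DLT is enough for the model update (3.1, 3.1.2) |

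Rows 1 and 2 show 5.1 admitting too many patients. Row 4 shows 6.4 admitting too few, because its DLT exception covers incomplete administrations but not a missing echo.

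**2. Which rule governs.** SAP 7.4.1 estimates the MTD in the set as defined in Section 6.4. SAP 6.3 and Table 7.4.1:1 exclude non-DLT discontinuation, dose reduction, progression, death and events causing missed visits. Protocol 7.2.1 admits only evaluable patients. Under these rules the dilution from rows 1 and 2 is zero.

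**3. Size if 5.1 were applied**

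*Crude rates.* Two added patients: 2/6 = 33.3% becomes 2/8 = 25.0%. One added patient: 1/3 = 33.3% becomes 1/4 = 25.0%.

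*Single dose at the reference dose.* Inputs: the Table 7: 1 prior N(log 0.5, 2) with the second parameter read as an SD; between-trial SD 0.25 (the median of its prior); escalation allowed only if the overdose probability is below 25% (protocol Section 7). Slope, other doses and the 1381-0001 data are left out.

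logit(p) ~ N(log 0.5, √(2² + 0.25²) = 2.016); r ~ Binomial(n, p); the result is P(p ≥ 0.33 | r, n).

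| One patient added | Before | After | Crosses 25%? |
|---|---|---|---|
| 1/3 to 1/4 | 0.475 | 0.345 | no |
| 1/4 to 1/5 | 0.345 | 0.248 | yes, barely |
| 2/6 to 2/7 | 0.478 | 0.377 | no |
| 2/8 to 2/9 | 0.292 | 0.224 | yes |
| 2/9 to 2/10 | 0.224 | 0.170 | no, already below |

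If the second parameter is a variance, the SD is √(2 + 0.25²) = 1.436. Then 1/5 gives 0.275, so that step no longer crosses; 2/8 to 2/9 gives 0.309 to 0.241 and still does.

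*Single-agent BLRM with the Table 7: 1 priors.* The plan's one visible figure is Scenario 02 in protocol 10.5: overdose probability 0.656 after 1 DLT in 1 patient at 50 µg. The reference dose is redacted. Setting it to about 800 µg returns 0.656, which is a calibration and not an independent reproduction. Assumptions: 0/3 at 50 µg, a second level of 100 µg with 1/3 DLTs (Scenario 05), and no co-data.

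| Assumed reference dose | P(overdose at 200 µg), 1/3 | 1/4 | 1/5 | 1/6 |
|---|---|---|---|---|
| 400 µg | 0.391 | 0.330 | 0.280 | 0.240 |
| 800 µg | 0.298 | 0.241 | 0.196 | 0.160 |
| 1000 µg | 0.276 | 0.221 | 0.178 | 0.143 |

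The first and last columns agree with the protocol's account of Scenario 05 (no escalation) and Scenario 06 (200 µg allowed). One added patient crosses 25% at 800 and 1000 µg; at 400 µg it takes three.

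**4. The gap in 6.4.** If one of 2 DLT patients among 8 lacked the echo and were dropped, 2/8 = 25.0% would become 1/7 = 14.3%. This error also lowers the DLT rate, and unlike the first it changes the count of DLT patients.

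**The case against.** The strongest reply is that the SAP settles the matter itself. Section 7.4.1 names the 6.4 set, 6.3 and the estimand table exclude the typical case, and protocol 7.2.1 limits the MTD analysis to evaluable patients. Protocol 3.1.2 admits backfill patients to the main model only after a DLT or a full evaluation period. The SAP is dated after development was terminated, so it governs final reporting, not on-trial escalation. The crossing examples are also chosen at the step where crossing happens.

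Most of this stands. A reader might infer from 5.1 that unreplaced non-evaluable patients will be counted as DLT-free and that the planned DLT rate is diluted. The documents do not support that. A reader might also infer that protocol 3.3.4.1 keeps patients who stopped for non-DLT toxicity in the denominator. It does not: it governs replacement, and 3.3.4.4 makes anyone withdrawn for a reason other than a DLT non-evaluable.

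The reply does not remove the conflict:
- SAP 7.4.1 and protocol 7.2.2 still word the exclusion by replacement status.
- SAP 5.1 is the definition tied to a named data source, the replacement file, from which a programmer could build the flag.
- SAP 6.3 does not list a dose skipped at an attended visit, or a missed echo alone.
- Table 7.4.1:1 says excluded patients are also replaced, while protocol 3.3.4.4 allows that not to happen.

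**Conclusion.** The SAP is wrong as written: one name for the primary analysis set carries two definitions that can select different patients, and 5.1 contradicts protocol 3.3.4.4. The weight of the text favours 6.4, and dilution under that reading is zero.

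If 5.1 were programmed, one added non-DLT patient could reverse the overdose decision in some data patterns, such as 2/8 to 2/9, but not in most of the adjacent steps checked. These sizes rest on a single-dose or single-agent simplification, an assumed reference dose and dose grid, and no co-data. The number of non-evaluable, unreplaced patients is not given, so the actual effect cannot be stated. The missing DLT exception for the echo in 6.4 is a separate defect and holds on the literal text.

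**What to change.** 1. In SAP 5.1, delete the sentence that equates patients not replaced with the MTD set, and refer to SAP 6.4.
2. In SAP 6.4, extend the exception so that every patient with a DLT in the MTD evaluation period is kept, whatever the dosing or echo status.
3. In SAP 7.4.1 and protocol 7.2.2, exclude patients not evaluable under protocol 3.3.4.4, whether or not they were replaced. State the DLT exception there too, because the missed-dose and missed-echo conditions in 3.3.4.4 carry none of their own.
4. Reconcile the replacement reasons in protocol 3.3.4.1 and 3.3.4.4.
5. List non-evaluable, unreplaced patients by dose level and reason.

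The cost is wording in both documents, one derivation flag and one listing. There may be slightly fewer evaluable patients than under 5.1.

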## **5.2 SECONDARY ENDPOINT(S)**

### 5.2.1 Key secondary endpoint(s)

Not applicable, no key secondary endpoints have been specified in the CTP.

## 5.2.2 Secondary endpoint(s)

The secondary endpoints of this trial are:

For CTP Version 1 and 2:

- Objective response based on Response Evaluation Criteria in Solid Tumors (RECIST)
- Best percentage change from baseline in size of injected lesions
- Best percentage change from baseline in size of target lesions

[figure not shown]
Proprietary confidential information © 2024 Boehringer Ingelheim International GmbH or one or more of its affiliated companies.

## For CTP Version 3 and later:

Date: 8 Apr 2024, Version 1.0

- Objective response based on Response Criteria for Intratumoural Immunotherapy in Solid Tumours (itRECIST)
- Best percentage change from baseline in size of injected target lesions
- Best percentage change from baseline in size of non-injected target lesions

[figure not shown]
All secondary endpoints will be assessed separately for Arm A and Arm B.

Date: 8 Apr 2024, Version 1.0

c44138015-01

Proprietary confidential information © 2024 Boehringer Ingelheim International GmbH or one or more of its affiliated companies.

Proprietary confidential information © 2024 Boehringer Ingelheim International GmbH or one or more of its affiliated companies.

## 6. GENERAL ANALYSIS DEFINITIONS

## 6.1 TREATMENT(S)

In this Phase I trial treatments are not randomized. In Arm A and Arm B, different dose levels of BI 1387446 alone (Arm A) or of BI 1387446 in combination with 240 mg of ezabenlimab (Arm B) are being administered.

If not specified otherwise, all analyses will be performed for each treatment arm separately. Data will be presented by initial treatment, i.e. within each treatment arm for all dose cohorts separately and in total over all dose cohorts of that arm.

For safety summaries, events that start from the first administration of any trial medication until 90 days after the last administration of any trial medication (residual effect period, REP) will be assigned to the on-treatment period for evaluation. If not specified otherwise, all safety tables will be based on the on-treatment period. Adverse events that have an onset during the screening or the follow-up period will be displayed in separate listings from those that occurred during the on-treatment period.

The MTD evaluation period will be derived as the time from the first administration of study drug to the start of the second treatment cycle, i.e., in more detail as the time from the first administration of (any) trial medication to the start of the 2nd administration of ezabenlimab or 4th administration of BI 1387446 (whatever from the latter two comes first). In the case that the 2nd administration of ezabenlimab and/or the 4th administration of BI 1387446 are not given, the MTD evaluation period ends 90 days after the last administration.

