2.1.2 Primary endpoint(s)

[figure not shown]
- MTD based on number of Dose-limiting toxicities (DLTs) (for definition of MTD refer to [Section 7](#))
- Number of patients with DLT in the MTD evaluation period

[figure not shown]
Time frame: Arms A, B From start of treatment until end of cycle 1 (3 weeks, MTD evaluation period)

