4.1.4.4 Dose limiting toxicity

DLTs will be recorded throughout the trial. Only DLTs starting in the first cycle of monotherapy (Arm A), or during the first cycle of BI 1387446 in combination with ezabenlimab (BI 754091) (Arm B) are required for dose-escalation decisions made by the SMC. DLT information from later cycles will be taken into consideration if applicable.

Any of the following AEs will be classified as DLTs unless unequivocally due to underlying malignancy or an extraneous cause:

- A) Hematologic toxicity
 - 1) any grade 5 toxicity
 - 2) neutropenia grade 4 lasting for $>$ 5 days
 - 3) neutropenia grade \geq 3 with documented infection
 - 4) febrile neutropenia
 - 5) thrombocytopenia grade 4
 - 6) thrombocytopenia grade 3 with concomitant bleeding grade \geq 2 (i.e. bleeding requiring intervention)

B) Grade 4 anaemia

C) Non-haematological toxicity

- 1) AST or ALT >3 times ULN and concurrent total bilirubin >2 times ULN without initial findings of cholestasis (e.g. findings consistent with Hy's law or the FDA definition of potential DILI)
- 2) AST or ALT elevation grade ≥ 4
- 3) CRS grade ≥ 3
- 4) Any other \geq Grade 3 non-haematologic toxicity with the following exceptions:
 - a. Grade 3 irAE that resolves to \leq Grade 1 or to baseline with immunosuppressive therapy within 2 weeks
 - b. Grade 3 fatigue that persists <7 days
 - c. Grade 3 rash that resolves to \leq Grade 1 within 2 weeks
 - d. Grade 3 or 4 elevation in serum amylase and/or lipase that is not associated with clinical or radiographic evidence of pancreatitis
 - e. Grade 3 electrolyte abnormality that lasts <72 hours, is not clinically complicated, and resolves spontaneously or responds to conventional medical intervention
 - f. Grade 3 nausea or vomiting that lasts <48 hours, and resolves to \leq Grade 1 either spontaneously or with conventional medical intervention
 - g. Alopecia
 - h. Grade 3 endocrine disorders (thyroid, pituitary, and/or adrenal insufficiency) that are managed with or without systemic corticosteroid therapy and/or hormone replacement therapy, and the patient is asymptomatic.
 - i. Grade 3 tumour flare syndrome
- 5) Pneumonitis Grade 2
- 6) Any Grade 2 related uveitis, eye pain, or blurred vision that does not respond to topical therapy and does not improve to Grade 1 severity within 2 weeks or requires systemic treatment
- 7) Any Grade ≥ 2 toxicity that persists and results in a delay of >14 days of Cycle 2 Day 1.

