The frequency, time to onset, and severity of toxicities, as well as the success of standard medical management and dosing interruptions/delays, will be analysed to determine if a given toxicity not listed above should be considered a DLT for dose escalation purposes.

Late DLTs are AEs that meet the DLT criteria but occur on treatment after the completion of the initial MTD evaluation period (Arm A and B: Cycle 1, including echocardiographic/MUGA scan measurements acquired on Day 1 of Cycle 2 and related findings). If any late DLT is reported during dose escalation, the BLRM will be rerun using all DLTs, and updated results will be reviewed in the SMC meeting to recommend the next dose level and cohort size.

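### When cycle 2 is not given, the SAP ends the MTD evaluation period 90 days after the last dose; the protocol ends it with cycle 1 and the Cycle 2 Day 1 echo/MUGA

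*SAP*

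**What the plan says.** **Protocol.** Section 2.1.2 gives the time frame of both primary endpoints as "From start of treatment until end of cycle 1 (3 weeks, MTD evaluation period". Sections 3.1 and 4.1.4.4 add the echo/MUGA of Cycle 2 Day 1 and its related findings. Section 4.1.4.4 says which DLTs are required for escalation decisions: "Only DLTs starting in the first cycle of monotherapy (Arm A), or during the first cycle of BI 1387446 in combination with ezabenlimab". It also says: "Late DLTs are AEs that meet the DLT criteria but occur on treatment after the completion of the initial MTD evaluation period". Under section 7.2.2, "the main analysis of the MTD will use the joint 5-parameter BLRM model described above using DLT data from the MTD evaluation period", while analyses of all DLT data are sensitivity analyses.

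**SAP.** Section 5.1 first agrees: "The MTD evaluation period is defined as the first treatment cycle including echocardiographic/MUGA scan measurements acquired on Day 1 of Cycle 2". It then derives the period, and section 6.1 repeats the derivation: first dose of any trial drug to the second ezabenlimab or fourth BI 1387446 dose, whichever comes first. Both sections add a fallback for when "2nd administration of ezabenlimab and/or the 4th administration of BI 1387446 are not given, the MTD evaluation period ends 90 days after the last administration". The visible text gives no reason for it.

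The MTD set in SAP 6.4 consists of treated patients who "completed the required number of administrations of BI 1387446 (and ezabenlimab in arm B) in cycle 1 and who underwent the Echo/MUGA scan" at the first visit of cycle 2. Patients who fell short of the cycle 1 doses because of a DLT stay in. SAP 7.4.1 names this set for the main analysis and also applies the intercurrent-event strategy of SAP 6.3.

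**The concern.** SAP 5.1 defines the period one way and derives it another way for patients without cycle 2 dosing. The derivation is what will be programmed, and both primary endpoints (the number of patients with a DLT, and the MTD) depend on it. Following the SAP as written would give some patients a much longer observation window than the protocol allows. Events that the protocol keeps out of the main analysis could be counted in it.

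Dosing decisions are not at stake. During escalation the model was to be rerun with all DLTs whenever a late one was reported (Protocol 4.1.4.4), and development has been terminated (SAP 4). What is at stake is correct reporting of the primary endpoints.

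**Working it through.** **1. The protocol's own figure.** One cycle of 3 weeks: 3 × 7 = 21 days, which matches the stated 3 weeks. Cycle 2 Day 1 is then Day 22.

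**2. The SAP fallback.** End day = day of last dose + 90. The cycle 1 dosing days are redacted. Protocol 5.3.1 refers to weekly administration, and the SAP treats the fourth BI 1387446 dose as the start of cycle 2, so I assume doses on Days 1, 8 and 15.

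- End day: 15 + 90 = Day 105.
- Excess: 105 − 21 = 84 days, or 105 − 22 = 83 days counting the Day 22 echo/MUGA.
- Ratio: 105 / 21 = 5.0.

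The conflict itself does not need the assumption, because 90 days after any dose is longer than a 3-week period.

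**3. Who is affected.** The rule changes the DLT status only of MTD-set patients with all cycle 1 doses, the cycle 2 echo/MUGA, no cycle 1 DLT, no further dose and no cross-over.

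- Patients with a cycle 1 DLT already count once, and SAP 5.1 says: "Patients who experience a DLT will not be replaced". Their status does not change.
- Cross-over patients are not counted as affected. If Arm B doses count, their first Arm B injection is the fourth BI 1387446 dose and the fallback does not apply. Figure 6.1: 1, which might settle this, is not shown.
- If the end-of-treatment visit replaces the first cycle 2 visit (Flow Chart, footnote 3), the patient is in the MTD set only if that visit's echo counts. The SAP does not say whether it does.

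**4. Two readings of SAP 7.4.1.** If 6.4 governs, late DLTs of these patients enter the main analysis, against Protocol 7.2.2. If 6.3 governs, progression, non-DLT death or non-DLT discontinuation up to about Day 105 leads to exclusion, although these patients meet the evaluability conditions of Protocol 3.3.4.4 and SAP 6.4. Either way the result departs from the protocol.

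The mismatch between 6.3 and 6.4 exists without the fallback. The first scan may be 5 days early (Flow Chart, footnote 24), so progression can be recorded from Day 22 − 5 = Day 17, inside the protocol window. The fallback stretches that overlap from Days 17–21 to Day 105.

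**5. Weight of one patient.** Protocol 3.1.2 foresees 3 to 8 patients per higher dose level. Protocol 7 sets the target interval at [0.16, 0.33), a width of 0.33 − 0.16 = 0.17.

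| Change | Raw DLT proportion |
|---|---|
| One extra DLT among 8 | +1/8 = +12.5 points |
| One extra DLT among 3 | +1/3 = +33.3 points |
| 1/6 to 2/6 | 16.7% to 33.3% |
| 2/8 to 3/8 | 25.0% to 37.5% |
| One DLT-free patient excluded, 2/8 to 2/7 | 25.0% to 28.6% |

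These are raw proportions, not model output. The effect on the posterior cannot be computed, because the BI 1387446 reference dose, the dose grid and the 1381-0001 data are redacted.

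**6. Consistency of the analyses.** The likelihood in Protocol 7 is binomial with one DLT probability per dose combination. With the fallback, patients who continue contribute about 3 weeks and the others 105 / 7 = 15 weeks. For the latter, the main window equals the on-treatment window of the supplementary analysis in SAP 7.4.4.

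**7. The and/or wording.** Arm A receives no ezabenlimab. Read literally, the fallback therefore applies to every Arm A patient, which is presumably not intended.

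**The case against.** The strongest reply is that SAP 6.3 removes these patients anyway. They stopped treatment, and under the 90-day window that stop falls inside the MTD evaluation period. Unless they stopped because of a DLT, they are excluded together with any late DLT. It stands that the direction of the effect depends on which section prevails. The reply does not rescue the rule, because it replaces wrongly counted DLTs with wrongly excluded evaluable patients.

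Second, some DLT criteria need follow-up beyond Day 21. A toxicity that delays Cycle 2 Day 1 by more than 14 days cannot be established before about Day 22 + 14 = Day 36, and several exceptions depend on resolution within 2 weeks. True, but this concerns how an event is classified. Protocol 4.1.4.4 ties DLTs to onset in cycle 1, and nothing there supports counting new onsets for 90 days.

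Third, the SAP ends the period at the first cycle 2 dose even when cycle 2 is delayed. With a cap at the echo/MUGA, an onset on Day 28 would count for a patient dosed on Day 35 but not for one never re-dosed. That asymmetry is real, but it comes from the SAP's existing main rule, not from removing the fallback.

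Fourth, SAP 5.1 ties MTD-set membership to replacement decisions kept in a separate file, and Protocol 3.3.4.4 gives the SMC a say. So membership is not purely mechanical, but evaluable patients who were not replaced remain in the set.

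Finally, the shifts of 12.5 to 33.3 points are what any single DLT does in a small cohort, and the affected group may be empty. Both stand, and they limit the claim.

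**Conclusion.** The concern holds. The fallback in SAP 5.1 and 6.1 contradicts SAP 5.1's own definition and the protocol, and it misderives the window for both primary endpoints. For the affected patients the window is about 105 days instead of 21 or 22, assuming cycle 1 doses on Days 1, 8 and 15. One such patient could shift the raw DLT proportion at a dose by 12.5 to 33.3 points, assuming 3 to 8 patients per dose level. No effect on the MTD or on dosing is claimed, and the number of affected patients is unknown. The rule should be corrected so that the primary endpoints are reported as the protocol defines them.

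**What to change.** Change the SAP only:

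1. In 5.1 and 6.1, replace the 90-day sentence. If cycle 2 is not started, the period ends at the Cycle 2 Day 1 echo/MUGA, but not before the planned end of cycle 1 (Day 21). The second condition is needed because the echo may be done up to 72 hours early, from Day 22 − 3 = Day 19 (Flow Chart, footnote 34). If the assessment is not done, the period ends at the planned end of cycle 1. For cross-over patients it ends no later than the first Arm B dose.
2. Assign DLTs by onset date. Date findings from the Cycle 2 Day 1 echo/MUGA to that assessment; an LVEF decline is confirmed only 1–2 weeks later (Protocol 5.2.5) and would otherwise fall outside the period.
3. Word the end rule by arm. Arm A: fourth BI 1387446 dose. Arm B: the earlier of the second ezabenlimab and fourth BI 1387446 dose.
4. Separately, align the exclusions in 6.3 with the MTD set in 6.4 and state which prevails, keeping the rule that patients with a DLT are not replaced. State whether an end-of-treatment echo that replaces the first cycle 2 visit counts for 6.4.
5. Leave later DLTs to the supplementary analysis in 7.4.4.

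The cost is SAP wording and one derivation, with no new data or patients.
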